9.4 SUBJECT DEMOGRAPHICS AND BASELINE CHARACTERISTICS

Baseline demographic and clinical characteristics will be summarized as percentages for categorical variables and as mean, standard deviation, median, minimum and maximum for continuous measures. The analyses of baseline characteristics will be performed for the ITT population.

9.5 MEDICAL HISTORY

Medical history will be captured at the Screening visit.

9.6 EXTENT OF EXPOSURE

The dose (mg) of study drugs administered, the total number of doses of study drug, and the duration of treatment (number of study cycles) will be summarized with descriptive statistics. The number and percentage of subjects whose dose is modified at any time will be summarized by each type of modification by cycle and overall. The proportion of subjects completing each cycle of treatment will be summarized.

9.7 EFFICACY ANALYSES

Each subject will be assigned to one of the following categories: 1) complete response, 2) partial response, 3) stable disease, 4) progressive disease, 5) early death from malignant disease, 6) early death from toxicity, 7) early death because of other cause, or 8) unknown (not assessable, insufficient data).

Many of the efficacy measures will be based on disease assessments. The best clinical response as well as disease progression will be determined by the treating investigator. Scans should be kept on file in cases where independent review or confirmation may be warranted. Definitive disease progression will be based on standard criteria (Hallek et al. 2008, Appendix A – CLL Response Definition) occurring for any reason (e.g., increasing lymphadenopathy, organomegaly or bone marrow involvement; decreasing platelet count, hemoglobin, or neutrophil count; or worsening of disease-related symptoms) other than lymphocytosis.

Subjects will be treated until disease progression, unacceptable toxicity or the end of the study. Upon the end of the study, subjects without disease progression may be transitioned to an open label compassionate use study.

9.8 MISSING VALUE HANDLING PROCEDURES

In general, other than for partial dates, missing data will not be imputed and will be treated as missing. The algorithms for imputation of partial dates may vary depending upon the parameter.

9.9 STATISTICAL ANALYSES

9.9.1 PRIMARY EFFICACY VARIABLE - PFS

The primary efficacy outcome is progression-free survival (PFS). Time to progression event "Survival" curve will be presented using Kaplan-Meier method. Median time to event and the 95% confidence interval of the median times will be presented, if estimable. Median time to event will be tested against the null hypothesis value using a one-sample (one-sided) log-rank test.

PFS is defined as the interval from Cycle 1/Day 1 to the earlier of the first documentation of definitive disease progression or death from any cause.

9.9.2 SECONDARY EFFICACY OUTCOMES

Secondary efficacy outcomes will include:

- Overall Response Rate (ORR)
- Time to Treatment Failure (TTF)
- Duration of Response (DOR)

9.9.2.1 OVERALL RESPONSE RATE

Overall Response Rate (ORR) will be determined according to the criteria of the International Workshop on Chronic Lymphocytic Leukemia (Hallek et al. 2008).

We will estimate Overall Response Rate (ORR), is defined as percent of subjects who achieve CR or PR. We will also estimate exact 95% confidence intervals for the response rates. These will be followed by additional logistic regression analyses model to adjust for demographic and baseline parameters.

9.9.2.2 TIME TO TREATMENT FAILURE

Time to Treatment Failure (TTF) is defined as a composite endpoint measuring time from Cycle 1/Day 1 to discontinuation of treatment for any reason, including disease progression, treatment toxicity, and death. Estimates of median TTF will be made using Kaplan-Meier methods.

9.9.2.3 DURATION OF RESPONSE

Duration of response (DOR) defined as the interval from the first documentation of CR or PR to the earlier of the first documentation of definitive disease progression or death from any cause. This variable will be summarized. Estimates of median DOR will be made using Kaplan-Meier methods.

10 SAFETY REPORTING AND ANALYSIS

10.1 SAFETY ANALYSES

Safety evaluations will be based on the incidence, intensity, and type of adverse events, as well as on clinically significant changes in the subject's physical examination, vital signs, and clinical laboratory results. Safety analyses will be performed using the safety population. Safety variables will be tabulated and presented by the dose of umbralisib study drug actually received. Exposure to study treatment and reasons for discontinuation of study treatment will also be tabulated.

10.2 ADVERSE EVENT CHARACTERISTICS

CTCAE term (AE description) and grade: The descriptions and grading scales found in the revised NCI Common Terminology Criteria for Adverse Events (CTCAE) version 4.0 will be utilized for AE reporting. All appropriate treatment areas should have access to a copy of the CTCAE version 4.0. A copy of the CTCAE version 4.0 can be downloaded from the CTEP web site http://ctep.cancer.gov/protocolDevelopment/electronic applications/ctc.htm.

'Expectedness': AEs can be 'Unexpected' or 'Expected' for expedited reporting purposes only. Expected AEs are defined as those described in the umbralisib Investigator Brochure.

Definitions of Adverse Events

An adverse event (AE) is any untoward medical occurrence in a subject or clinical investigation subject administered a pharmaceutical product. An AE does not necessarily have to have a causal relationship with this treatment. An adverse event (AE) can therefore be any unfavorable and unintended sign (including an abnormal laboratory finding, for example), symptom, or disease temporarily associated with the use of a medicinal product, whether or not considered related to the medicinal product. This includes any occurrence that is new in onset or aggravated in severity or frequency from the baseline condition.

In clinical studies, an AE can include an undesirable medical condition occurring at any time, including run-in or washout periods, even if no study treatment has been administered. The NCI Common Terminology Criteria for Adverse Events (CTCAE) v4.0 is to be used for the grading of severity of symptoms and abnormal findings. For adverse events not covered by the NCI-CTCAE Version 4.0 grading system, the following definitions will be used:

- Grade 1: Mild; asymptomatic or mild symptoms; clinical or diagnostic observations only; intervention not indicated.
- · Grade 2: Moderate; minimal, local or non-invasive intervention indicated.
- Grade 3: Severe or medically significant but not immediately life-threatening; hospitalization or prolongation of hospitalization indicated.
- Grade 4: Life-threatening consequences; urgent intervention indicated.
- Grade 5: Death related to AE.

TGR-1202-201-CLL

Dated: 05 March 2019 (Ver. 5.0) Page 47 of 71

10.3 ADVERSE EVENTS (AE'S) AND TREATMENT EMERGENT ADVERSE EVENTS (TEAE'S)

All AEs and SAEs occurring on study will be listed by subject. The frequency and percentages of subjects with treatment-emergent adverse events (TEAEs) will be tabulated by system organ class (SOC) and preferred term (PT), where treatment-emergent is defined as any AE that:

- Occurs after first dosing of study medication (Cycle 1/Day 1) and through the end of the study or up through 30 days (+/-7 days) after the last dose of study treatment, or
- · Is considered treatment-related regardless of the start date of the event, or
- Is present before first dosing of study medication but worsens in intensity or the investigator subsequently considers treatment-related.

TEAEs that are considered at least possibly related to study treatment will be tabulated as well as deaths, SAEs, and events resulting in treatment discontinuation.

AEs that occur after informed consent but before first dosing of study medication will not be summarized but will be listed.

At each level of summarization, a subject will be counted only once for each AE, SOC, or PT experienced within that level. In the summation for AE severity, within each level of AE, SOC, or PT experienced, the one with the highest severity will be included. In the summation for AE's relationship to the study drug, within each level of AE, SOC, or PT experienced, the one with the closest relationship to the study drug will be included.

10.4 ADVERSE EVENTS / SERIOUS ADVERSE EVENT CAUSALITY ASSESSMENT

The Investigator must also assess the relationship of any adverse event to the use of study drugs (whether none, one, or both), based on available information, using the following guidelines:

- Not Related: Clear-cut temporal and/or mechanistic relation to a cause other than the study drug(s).
- Doubtful: There is no reasonable possibility that the event is related to the study drug(s) but
 a definite cause cannot be ascertained.
- Possible: There is still a reasonable possibility that the cause of the event was the study drug(s) but there exists a more likely cause of the event such as complications of progressive disease.
- Probable: The most likely cause of the event is the study drug(s) but other causes cannot be completely excluded.
- Definite: Clear cut temporal and/or mechanistic relation to the study drug(s). All other
 causes have been eliminated. Events classified as definite will often be confirmed by
 documenting resolution on discontinuation of the study drug and recurrence upon
 resumption.

10.4.1 RECORDING OF ADVERSE EVENTS

All adverse events of any subject during the course of the study will be reported on the case report form, and the investigator will give his or her opinion as to the relationship of the adverse event to

TGR-1202-201-CLL

study drug treatment (i.e., whether the event is related or unrelated to study drug administration – umbralisib). If the adverse event is serious, it should be reported as soon as possible and no greater than 24 hours to the sponsor or designee. Other untoward events occurring in the framework of a clinical study are also to be recorded as AEs (i.e., AEs that occur prior to assignment of study treatment that are related to a protocol-mandated intervention, including invasive procedures such as biopsies, medication washout, or no treatment run-in).

All AEs regardless of seriousness or relationship to umbralisib treatment spanning from Cycle 1/Day 1 until 30 calendar days (+/-7 days) after discontinuation or completion of either protocol-specific treatment as defined by the protocol for that subject, are to be recorded on the eCRF.

10.4.2 ABNORMAL LABORATORY VALUES AND VITAL SIGNS

The reporting of abnormalities of vital signs as adverse events should be avoided. Abnormalities of vital signs should not be reported unless any criterion for an SAE is fulfilled, the vital signs abnormalities cause the subject to discontinue study treatment, or the investigator insists that the abnormality should be reported as an AE. Abnormal laboratory results should be noted in the eCRF as an adverse event if they are associated with an overdose, require or prolong inpatient hospitalization, or are otherwise considered clinically significant by the investigator. If an abnormal laboratory value or vital sign is associated with clinical signs and/or symptoms, the sign or symptom should be reported as an AE, and the associated laboratory value or vital sign should be considered additional information that must be collected in the relevant eCRF. If the laboratory abnormality is a sign of a disease or syndrome, only the diagnosis needs to be recorded on the SAE Report Form or AE eCRF.

Clinical Laboratory Results will be summarized. Summary statistics for actual values and for changes from baseline will be tabulated for laboratory results by scheduled visit. Subjects with laboratory values outside of the normal reference range at any post-baseline assessment will be summarized, and graded per NCI CTCAE Version 4.0 when applicable. Subject incidence of abnormal laboratory results will be summarized by treatment group and maximum grade for each abnormal laboratory finding.

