2 OBJECTIVES AND ENDPOINTS

2.1 STUDY OBJECTIVES

PRIMARY OBJECTIVE

 To determine the progression free survival of umbralisib in patients who were intolerant to prior BTK and/or PI3K-delta inhibitors.

KEY SECONDARY OBJECTIVES

- To evaluate the overall response rate (CR + PR) and duration of response of umbralisib in patients who were intolerant to prior BTK and/or PI3K-delta inhibitors.
- To evaluate Time to Treatment Failure with umbralisib as compared to the prior kinase inhibitor therapy in patients with CLL.
- To evaluate the safety profile of umbralisib as compared to the safety profile of the prior kinase inhibitor therapy in patients with CLL.

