3.1 INCLUSION CRITERIA

Patients must meet all of the following inclusion criteria to be eligible for participation in this study:

- 1. Confirmed diagnosis of CLL as per the iwCLL (Hallek 2008) criteria
- CLL warranting therapy as per investigator discretion.
- 3. Patients must be off prior BTK and/or PI3K-delta inhibitor for at least 14 days following discontinuation without documented disease progression. This is to ensure the reason for discontinuation was intolerance, not disease progression as listed below, # 4 7. Patients may sign consent during the washout period.
- 4. For ibrutinib/BTK patients who experience related hematologic and non-hematologic toxicities and discontinue therapy (see bullet 7). Non-hematologic toxicities are limited to: Atrial fibrillation, Hypertension, Bleeding, Arthralgia, Rash, Diarrhea, Infection, Pneumonitis.
- For idelalisib/duvelisib patients who experience related hematologic and non-hematologic toxicities and discontinue therapy (see bullet 7). Non-hematologic toxicities are limited to: Pneumonitis, Transaminitis, Rash, Colitis, and Infection.
- 6. Other grade ≥ 2 non-hematologic toxicities not listed in 4 or 5, despite dose interruption and/or reduction, and defined by the treating investigator as "intolerant", will be evaluated individually by the study chair as part of eligibility criteria as part of the screening process.
- Prior therapy with a BTK inhibitor (ibrutinib, ACP-196, other) or a PI3K-delta inhibitor (idelalisib, duvelisib, other) which was discontinued, due to intolerance, within 12 months of the time of treatment initiation with umbralisib (Cycle 1/Day 1).
 - a. Intolerance defined as unacceptable toxicity where in the opinion of the investigator, treatment should be discontinued in spite of optimal supportive care as a result of one of the following:
 - i. ≥ 2 Grade ≥ 2 non-hematological toxicities (see list above, #4-6) as a cause of discontinuation, and/or;
 - ii. ≥ 1 Grade ≥ 3 non-hematological toxicity (see list above, #4-6), and/or;
 - iii. ≥ 1 Grade 3 neutropenia with infection or fever, and/or;
 - iv. Grade 4 hematological toxicities, AND the toxicities persistent to the point that the investigator chose to discontinue therapy due to toxicity / not progression.
 - v. Toxicity must resolve to ≤ grade 1 prior to umbralisib dosing.
- 8. Adequate organ system function, defined as follows:

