10.8.1 PERSISTENT OR RECURRENT ADVERSE EVENTS

A persistent AE is one that extends continuously, without resolution, between subject evaluation time points. Such events should only be recorded once on the SAE Report Form and/or the AE eCRF. If a persistent AE becomes more severe (changes from a Grade 1 or 2 AE to a Grade 3 or 4 AE) or lessens in severity (changes from a Grade 3 or 4 AE to a Grade 1 or 2 AE), it should be recorded on a separate SAE Report Form and/or AE eCRF.

A recurrent AE is one that occurs and resolves between subject evaluation time points, and subsequently recurs. All recurrent AEs should be recorded on an SAE Report Form and/or AE eCRF for each recurrence.

TGR-1202-201-CLL

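### Section 10.4.2 may keep asymptomatic blood-pressure rises out of the adverse-event tables, and Section 10.8.1 does not secure the maximum grade of a persistent event

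*Combined protocol and SAP*

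**What the plan says.** All references are to the combined protocol and SAP.

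- **Vital signs (10.4.2).** The default is that "The reporting of abnormalities of vital signs as adverse events should be avoided". It is lifted in three cases only. Two are automatic: the change meets an SAE criterion, or it ends treatment. The third is an override, worded as "the investigator insists that the abnormality should be reported as an AE". Accompanying symptoms are still captured: "If an abnormal laboratory value or vital sign is associated with clinical signs and/or symptoms, the sign or symptom should be reported as an AE".
- **Laboratory values (10.4.2).** These have a wider route. They are entered as adverse events if, among other reasons, they "are otherwise considered clinically significant by the investigator". They also get a by-visit summary and a table by maximum CTCAE grade. No such analysis is specified for vital signs.
- **Persistent events (10.8.1).** One record is made. A separate record is required "If a persistent AE becomes more severe (changes from a Grade 1 or 2 AE to a Grade 3 or 4 AE"), or on the reverse move. No other grade change is named.
- **Eligibility (3.1, criterion 4).** For prior BTK inhibitors: "Non-hematologic toxicities are limited to: Atrial fibrillation, Hypertension, Bleeding, Arthralgia, Rash, Diarrhea, Infection, Pneumonitis".
- **Objective (2.1).** A key secondary objective is: "To evaluate the safety profile of umbralisib as compared to the safety profile of the prior kinase inhibitor therapy in patients with CLL".

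**The concern.** The trial enrols people who stopped a kinase inhibitor because of toxicity, so one of its main safety questions is whether such toxicity appears on umbralisib. Hypertension is one of the toxicities that can qualify a subject, and blood pressure is a scheduled measurement. Yet the recording rule steers sites away from entering a blood-pressure rise as an adverse event unless it is serious or stops treatment, or the investigator presses the point. The adverse-event tables could then show little hypertension because of the reporting instruction.

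The second weakness concerns grade. The severity tables take the worst grade per subject and term, but the recording rule does not ensure that the worst grade reaches the database. Both matter for the umbralisib safety description itself, with or without a comparison with prior therapy.

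**Working it through.** The point rests on recording rules, and the plan states no figure that could be reproduced. The check sets the sections side by side.

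**1. Does the vital-sign rule conflict with other sections?**

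- Section 10.2 counts any unfavourable sign as an adverse event, including one that appears or worsens relative to baseline.
- Section 10.4.1 requires all adverse events, serious or not and related or not, on the eCRF from Cycle 1/Day 1 until 30 days after treatment ends.
- Section 10.1 bases safety evaluation partly on clinically significant vital-sign changes.
- Section 10.4.2 sets non-reporting as the default for vital signs.

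A site cannot follow 10.2, 10.4.1 and 10.4.2 together for an asymptomatic, non-serious blood-pressure rise. On a plain reading, a rise that leads only to a temporary hold of study drug or an added medication meets none of the automatic exceptions. It is then recorded only if the investigator insists.

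**2. Which listed toxicities does the vital-sign rule reach?** The Section 5 schedule lists weight, temperature, blood pressure, heart rate and respiratory rate. Set against criteria 4 and 5 of Section 3.1, the direct match is hypertension: one of eight BTK-inhibitor toxicities and none of the five listed for idelalisib/duvelisib.

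**3. Is there another route into the analysis?** Blood pressure is measured from screening through the end-of-treatment visit (Section 5), and Section 9.2 promises listings of all available safety data. The readings therefore exist, but no graded vital-sign summary is specified.

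**4. What does the grade-change rule miss?** There are six upward moves between Grades 1 and 4:

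- Crossing from 1–2 to 3–4, new record required: 1→3, 1→4, 2→3, 2→4.
- Not crossing, no new record named: 1→2 and 3→4.

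Section 10.3 tabulates the highest severity and counts each subject once per term. If the single record keeps its onset grade:

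- Any-grade counts are unchanged.
- Grade ≥3 counts are unchanged, because an event that reaches Grade 3 or more either starts there or crosses and gets its own record.
- Grade ≥2 counts can be too low (1→2), and Grade 4 counts can be too low (3→4).

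The documents do not say whether the record is updated. Laboratory abnormalities are protected by the separate table by maximum grade in 10.4.2. Events without a laboratory value, such as rash, diarrhea, arthralgia and bleeding, are not.

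**5. Scale.** With up to 55 subjects, one unrecorded subject lowers an incidence by 1/55 = 1.8 percentage points. No event rate or capture rate is given. For illustration only, recorded subjects = 55 × true rate × capture fraction:

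| Assumed true Grade ≥2 rate | True subjects | Recorded at 75% capture | Recorded at 25% capture |
|---|---|---|---|
| 5% | 2.8 | 2.1 | 0.7 |
| 10% | 5.5 | 4.1 | 1.4 |
| 20% | 11.0 | 8.2 | 2.8 |

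These rates and fractions are assumptions and do not predict what will happen in this trial.

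**The case against.** The strongest reply is that the protocol leaves several routes open, and most of it stands.

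- **Diagnosed hypertension is recordable.** Section 10.8 has a recognised condition named as the event. The investigator can override the vital-sign default, and symptoms are reported in any case.
- **Residual toxicity is covered.** A subject may enter with Grade 1 toxicity (criterion 7.a.v), but Section 10.8.5 records a pre-existing condition that worsens, and 10.3 counts it as treatment-emergent. An event that resolves and returns is recorded each time under 10.8.1. The grade gap is therefore confined to events that begin on study and persist.
- **Updating the grade is not forbidden.** A reader might infer that sites are told not to capture a move from Grade 1 to 2. Section 10.8.1 is silent on this, and the highest-severity tabulation in 10.3 is compatible with updating the record.
- **A single Grade 2 event is not the intolerance threshold.** A reader might treat it as such. For non-hematologic toxicity, criterion 7 asks for at least two at Grade ≥2 or one at Grade ≥3, and the move into Grade 3 is the one that 10.8.1 captures.

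These points limit the claim without removing it. Sections 10.8 and 10.8.5 pull against 10.4.2, but nothing says which prevails for a blood-pressure reading with no symptoms and no diagnosis. Capture then depends on which section a site follows. The investigator override is also a higher bar than the clinical-significance test for laboratory values in the same section.

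**Conclusion.** The conflict is real and should be resolved. Followed literally, Section 10.4.2 may leave asymptomatic, non-serious blood-pressure rises out of the adverse-event tables. Section 10.8.1 may leave the tabulated grade of an on-study persistent event too low for rises from 1 to 2 and 3 to 4. Both are risks of under-counting whose size cannot be derived from the documents. The second rests on the assumption that the record keeps its onset grade.

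Two stronger readings are not supported. A reader might infer that the listed intolerance toxicities in general are suppressed, but the vital-sign rule reaches only hypertension among them. A reader might also infer a bias in umbralisib's favour in the comparison with the prior inhibitor. The synopsis uses prior-treatment adverse events only where data exist and gives no rule for how they were captured. They may be under-recorded too, so the direction cannot be established.

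The point is a cheap improvement to safety recording. It does not touch the primary analysis.

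**What to change.** 1. **Section 10.4.2.** Give vital signs the same clinical-significance route as laboratory values. In addition, record as a graded adverse event any vital-sign change of CTCAE v4.0 Grade 2 or higher that corresponds to a toxicity in inclusion criteria 4–6 (in practice hypertension). Reconcile the wording with Sections 10.1, 10.2, 10.4.1, 10.8 and 10.8.5.
2. **Section 10.8.1.** Require each adverse-event record to carry its maximum grade, so that the tabulation in 10.3 has the input it assumes.
3. **Analysis.** Add a CTCAE-graded blood-pressure summary from the scheduled vitals, and a table of recurrence of each subject's qualifying toxicity at Grade 2 or higher on umbralisib.

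The cost is amendment wording, eCRF completion guidance and two tables. No assessment is added, because blood pressure is already on the schedule. The downside is a few more low-grade entries and a possibly less favourable adverse-event table.

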 - Absolute neutrophil count (ANC) ≥ 1,000 / platelet count ≥ 30,000. Growth factors are permitted at any time during the study.
 - b. Total bilirubin ≤1.5 times the upper limit of normal (ULN)
 - c. Alanine aminotransferase (ALT) and aspartate aminotransferase (AST) ≤2.5 x ULN if no liver involvement or ≤5 x the ULN if known liver involvement
 - d. Calculated creatinine clearance >30 mL/min (as calculated by the Cockcroft-Gault or MDRD formula, 24- hour urine Cr clearance also acceptable)
- ECOG performance status ≤ 2
- 10. Male or female ≥ 18 years of age
- 11. Ability to swallow and retain oral medication

TGR-1202-201-CLL

- 12. Female patients who are not of child-bearing potential and female patients of child-bearing potential who have a negative serum pregnancy test within 3 days prior to Cycle 1, Day 1.
- Willingness and ability to comply with trial and follow-up procedures, and give written informed consent.

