⁶ Baseline CT scan within 30 days prior to Cycle 1/Day 1; then during cycles 3, 6, 9, 12 and at least every 6 cycles for 24 cycles, then every 12 cycles thereafter or more frequent if warranted (+/- 14 days). CT imaging should be performed at EOT visit if it hasn't been completed within past 30 days.

⁷ If discontinued due to reasons other than progression, follow up every 3 months on status of disease progression. Patients who discontinue from study

⁷ If discontinued due to reasons other than progression, follow up every 3 months on status of disease progression. Patients who discontinue from study treatment after cycle 12 (for reasons other than disease progression) should be followed for progression, approximately every 6 months for 24 months then every 12 months or more frequent if warranted.

⁸ Serum pregnancy test within 72 hours prior to starting treatment on Cycle 1 / Day 1.

⁹ Urine pregnancy test within 72 hours of Day 1 of each cycle. Administer test with each drug dispensation after Cycle 6.

¹⁰ Peripheral Blood (screening, Cycle 2/Day 1 and at disease progression) and buccal swab (screening only) samples for correlative analyses. See lab manual.

¹¹ Additional peripheral blood sample will be collected at screening only and analyzed at central lab for high-risk cytogenetics as well as BTK/PI3K resistance and activating mutations/deletions of prognostic value.

¹² Bone Marrow aspirate/ biopsy performed at baseline at the discretion of investigator to evaluate cytopenias. Bone marrow to be repeated if patient meets clinical criteria for CR to confirm this finding, as per iwCLL criteria.

¹³ Subjects who discontinue study drug should have a follow up visit or telephone call to assess for AEs. This should be done 30 days (+/- 7 days) after the last dose of study drug. In addition, SAEs will be reported for 30 days after the last dose of study drug.

Laboratory assessments will be collected as specified in the study assessments and treatment schema. Please refer to the study/lab manual for instructions outlining collection and shipment procedures for lab samples for central review.

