8.6 PARTIAL RESPONSE

To satisfy criteria for a PR, all of the following criteria must be met:

- No evidence of new disease
- A change in disease status meeting ≥2 of the following criteria, with 2 exceptions in which
 only 1 criterion is needed: 1) only lymphadenopathy is present at baseline; 2) only
 lymphadenopathy and lymphocytosis are present at baseline. In these 2 cases, only
 lymphadenopathy must improve to the extent specified below:
 - In a subject with baseline lymphocytosis (ALC ≥4 x 10⁹/L), a decrease in peripheral blood ALC by ≥50% from baseline or a decrease to <4 x 10⁹/L
 - A decrease by ≥50% from the baseline in the SPD of the target nodal lesions (if applicable)
 - In a subject with enlargement of the spleen at baseline, a splenomegaly response as defined in Section 8.3.2
 - In a subject with enlargement of the liver at baseline, a hepatomegaly response as defined in Section 8.3.2
 - A decrease by ≥50% from baseline in the CLL marrow infiltrate or in B-lymphoid nodules
- No target, splenic, liver, or non-target disease with worsening that meets the criteria for definitive PD
- Peripheral blood counts meeting 1 of the following criteria:
 - ANC >1.5 x 10⁹/L or >50% increase over baseline without need for exogenous growth factors (e.g., G-CSF)
 - Platelet count ≥100 x 10⁹/L or ≥50% increase over baseline without need for exogenous growth factors
 - Hemoglobin ≥110 g/L (11.0 g/dL) or ≥50% increase over baseline without red blood cell transfusions or need for exogenous growth factors (e.g., erythropoietin)

The proportion of subjects who achieve a PR with lymphocytosis will be recorded.⁷

TGR-1202-201-CLL

To satisfy criteria for SD, the following criteria must be met:

- No evidence of new disease
- There is neither sufficient evidence of tumor shrinkage to qualify for PR nor sufficient evidence of tumor growth to qualify for definitive PD

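### Laboratory abnormalities are counted from any out-of-range post-baseline value at maximum grade, without reference to baseline grade, so abnormalities already present at entry enter the on-study incidence

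*Combined protocol and SAP*

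**What the plan says.** Section 10.4.2 plans three laboratory summaries.

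- Values and changes over time: "Summary statistics for actual values and for changes from baseline will be tabulated for laboratory results by scheduled visit".
- A count of subjects: "Subjects with laboratory values outside of the normal reference range at any post-baseline assessment will be summarized", graded by CTCAE v4.0 where a grade exists.
- Incidence by grade: "Subject incidence of abnormal laboratory results will be summarized by treatment group and maximum grade for each abnormal laboratory finding".

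The second and third set no condition on the baseline value or grade. No shift table and no treatment-emergent definition for laboratory values appears in the documents.

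Other sections show that abnormal values at entry are expected. Inclusion criterion 8 in Section 3.1 reads "Absolute neutrophil count (ANC) ≥ 1,000 / platelet count ≥ 30,000". It also allows bilirubin up to 1.5 x ULN and ALT/AST up to 2.5 x ULN, or 5 x ULN with liver involvement, and it has no hemoglobin item. Toxicity from the prior inhibitor may persist at grade 1: "Toxicity must resolve to ≤ grade 1 prior to umbralisib dosing". A footnote to the Section 5 schedule foresees low counts at entry: "Bone Marrow aspirate/ biopsy performed at baseline at the discretion of investigator to evaluate cytopenias". Section 8.6 names a baseline state directly: "In a subject with baseline lymphocytosis".

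For adverse events, Section 10.3 does use a baseline reference. A pre-existing event is treatment-emergent if it "Is present before first dosing of study medication but worsens in intensity", or if it is judged treatment-related. Section 10.1 rests the safety evaluation partly on clinically significant changes in laboratory results.

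**The concern.** The incidence tables measure the presence of an abnormality after baseline, whereas Section 10.1 says that safety is judged on change. In previously treated CLL the two can differ widely, because the analytes affected by the disease and by earlier therapy are also those in which drug effects are reported. Section 7.1.1 lists neutropenia as very common with umbralisib, and anaemia, thrombocytopenia, lymphocytosis and raised ALT and AST as common.

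The trial has one arm, so no control group shows the background rate. Someone reading a row of the incidence table could not tell how much of it was present on Cycle 1/Day 1. Safety relative to the prior kinase inhibitor is a key secondary objective, so these tables will be read for more than completeness.

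**Working it through.** The plan states no figure on this point, so there is none to reproduce. The check applies the rule to possible subject histories and then works out the size of the excess under stated assumptions.

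**Step 1. Can subjects enter with abnormal values?** Yes. Appendix A uses 1,500/µL for neutrophils and 100,000/µL for platelets as response thresholds. The entry floors are 1,000 and 30,000 (units not printed; taken here as per µL), which are below both. The bilirubin and transaminase limits are multiples of ULN above 1. Hemoglobin has no limit.

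**Step 2. How does the rule treat each history?**

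| Baseline | After baseline | Counted under 10.4.2 | Grade higher than baseline |
|---|---|---|---|
| Normal | Abnormal | Yes | Yes |
| Abnormal | Worse grade | Yes | Yes |
| Abnormal | Same grade | Yes | No |
| Abnormal | Better, still out of range | Yes | No |

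The last two rows are the problem. One out-of-range assessment is enough, so a subject who later returns to normal can also be counted.

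Example: a platelet count rising from 40,000 to 60,000 is a 50% increase (20,000/40,000) and meets the platelet item of the partial-response criteria in Section 8.6. If the local lower limit of normal is above 60,000, the same subject is counted as having an on-study platelet abnormality.

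**Step 3. Do the other planned outputs show the same thing?** Changes by visit summarize the distribution of values and do not give the number of subjects whose grade rose. Under Sections 10.4.2 and 10.8.2 a laboratory result becomes an adverse event if it is associated with overdose, requires or prolongs hospitalization, or is judged clinically significant by the investigator. Otherwise it enters through an associated symptom or diagnosis. The laboratory tables are thus the only planned subject-level grade summary covering all values.

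**Step 4. Size.** For one analyte, let

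- b = share abnormal at baseline and out of range again after baseline;
- w = share of those whose worst grade exceeds the baseline grade;
- q = share of the remaining subjects who develop an abnormality.

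All three are assumptions; the documents give none of them. N = 55 is the planned maximum enrollment (Section 4.1).

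- Incidence under the rule: b + (1 − b)q
- Incidence of new or worsened grade: bw + (1 − b)q
- Excess: b(1 − w)

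The excess does not depend on q. With w = 20%:

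- b = 20%: 0.20 × 0.80 = 16 points, or 0.16 × 55 = 8.8 subjects
- b = 40%: 0.40 × 0.80 = 32 points, or 0.32 × 55 = 17.6 subjects

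One full case with b = 30%, q = 20%, w = 20%: the rule gives 0.30 + 0.70 × 0.20 = 44% (24.2 subjects). New or worsened grade gives 0.30 × 0.20 + 0.70 × 0.20 = 20% (11.0 subjects). The ratio is 2.2.

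Over b = 10–50%, q = 10–20% and w = 10–20%, the ratio runs from 1.4 (28%/20%, at b = 10%, q = 20%, w = 20%) to 5.5 (55%/10%, at b = 50%, q = 10%, w = 10%).

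**The case against.** The strongest reply is that Section 10.4.2 describes abnormal laboratory results, does not call them toxicity or treatment-emergent, and reports what it says. Baseline is not ignored altogether: changes from baseline are planned by visit, Section 9.2 adds minimum, maximum and percentiles, and all safety data are to be listed. Clinically significant findings reach the adverse event tables, where Section 10.3 applies a baseline rule and Section 10.4 a causality assessment. What remains is one table format, derivable from planned data, in a descriptive analysis.

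Most of this stands, and it limits the point. It does not remove it: listings and visit-level summaries leave the reader to reconstruct who worsened, and the adverse event route depends partly on investigator judgment.

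Four stronger inferences are tempting but unsupported.

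- **The laboratory rule contradicts Section 10.3.** That section governs adverse events only. The approaches differ, but the texts do not conflict. Section 10.1 is the better comparison.
- **Laboratory effects could not be attributed to umbralisib at all.** Related treatment-emergent events are tabulated separately. Counting grade increases would not settle attribution either, since progressing CLL also lowers counts (Section 8.8).
- **The lymphocyte row would be near 100% whatever the drug does.** Section 8.6 treats baseline lymphocytosis as conditional and foresees subjects with lymphadenopathy only.
- **The excess equals the full baseline abnormality rate.** That holds only if every such abnormality is seen again and none worsens, so it is an upper bound. The grade 1 limit on residual prior toxicity also restrains part of the carry-over, though not CLL-related cytopenia.

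**Conclusion.** The point holds for the two incidence summaries in Section 10.4.2. As written, they count every baseline abnormality that is seen again after baseline, whether or not its grade rose. This sits poorly with the reliance on laboratory changes in Section 10.1.

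The direction is certain for any analyte with at least one persistent, unworsened baseline abnormality. The amount is unknown; the 16–32 points and the 1.4 to 5.5 ratio rest wholly on the assumed b, w and q. The consequence is confined to descriptive safety tables. The PFS test, the response and progression criteria and the treatment-emergent adverse event tables are untouched. The change is worth making because it is cheap and the present tables are easy to misread in a single-arm trial.

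**What to change.** In Section 10.4.2 or a separate SAP:

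1. Define laboratory incidence as a worst post-baseline CTCAE grade higher than the baseline grade, tabulated by worst grade.
2. State which pre-dose value is baseline. Hematology and chemistry are drawn both at screening and on Cycle 1/Day 1.
3. Add shift tables from baseline grade to worst post-baseline grade for ANC, platelets, hemoglobin, ALT, AST, bilirubin and creatinine.
4. Summarize lymphocytosis separately, using the description in Section 8.10: a rise of at least 50% from baseline and a count above 5,000/mcL.

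The existing out-of-range summary may stay as a supplement if its title says that it includes abnormalities present at baseline. The cost is SAP wording and some additional programming. The Section 5 schedule already provides the data.
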